Study Title: A More Physiological Feeding Process in ICU:the Intermittent Infusion With Semi-solidification of nutrients

ClinicalTrails.gov ID: NCT 03017079

Date: 11/24/2016

Responsible party: [name]

Email: [contact]

Statistical Analysis Plan

Data were expressed as means \pm standard deviations (SD) for quantitative variables and proportions for categorical and binary variables. Student's t test was used for statistical comparison between groups for continuous variables, general linear model for repeated measurement data, Fisher exact tests for categorical variables, and Mann-Whitney U test for ordinal variables. All tests for statistical significance were determined using an alpha level of 0.05. All analyses were performed using SPSS 17.0.

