Study Title: A More Physiological Feeding Process in ICU:the Intermittent Infusion With Semi-solidification of nutrients

ClinicalTrails.gov ID: NCT 03017079

Date: 11/24/2016

Responsible party: [name]

Email: [contact]

Study Protocol

一. Purpose

- 1) To investigate whether intermittent feeding with semi-solid nutrients improves the enteral nutrition complications of diarrhea, reflux and aspiration;
- 2) Observe the feeding intolerance and the efficiency of the EN of critically ill patients;
- 3) Observe the blood sugar and insulin secretion;

二. Design and method

(1) Single center, randomized, single blind, controlled prospective study;

(2) Inclusion criteria:

- 1) not less than 14 years old of critical illnesses;
- 2) No long-term history of oral administration of gastrointestinal motility drugs;
- 3) Nasogastric tube for enteral nutritional support treatment;
- 4) No acute pulmonary infection;
- 5) No previous history of upper gastrointestinal surgery;

(3) exclusion criteria:

- 1) Refuse into the study;
- 2) Stay in ICU less than 3 days
- 3) acute pulmonary infection before entering the ICU;
- 4) have nutritional contraindications, such as intestinal ischemia or obstruction, gastrointestinal hemorrhage and so on;
- 5) No enteral nutrition received for less than 3 days;

(4) Abort criteria:

- 1) Abandoning treatment and discharge, resulting in incomplete data
- 2) EN contraindications nutrition during treatment;
- 3) Other condition of researchers think that patients are not fit to continue with the study;

(5) Groups

[figure not shown]
- 1) intermittent feeding (IF)
- 2) intermittent feeding with semi-solid nutrients (IS)

If you are assigned to the IS group, you should first receive a package of semi-solid agent to increase the intestinal nutrition viscosity. If you are assigned to the IF group, you will receive the routine nutrition treatment, and the treatment time for both groups is 3 days. After 3 days, you will receive routine enteral nutrition therapy. If there were serious enteral nutrition complications such as aspiration and abdominal distension within 3 days, the experiment would end. The treatment of the two groups only depends on whether semi-solid agent was added, while the rest of the treatment measures were consistent.

(6) Test

Blood (Microvascular blood sugar+ C-peptide release test), Secretions from the posterior pharynx and trachea;

三. Study process

四. How to protect high-risk groups or vulnerable groups

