The subject of this study is critically illnesses. Before entering the research group, the researchers must obtain the informed consent by the patient or the agent authorizer about the specific content of the study. For details, please refer to the informed consent.

五. Sample Size Calculating

According to the literature reported, the incidence of gastrointestinal intolerance (FI) is about 30.8%. We presume that $\delta = -0.05$, $\alpha = 0.025$, $\beta = 0.20$, the non-inferior efficiency test design is

$$(n_1 = n_2 = \frac{(Z_{1-\alpha/2} + Z_{1-\beta})^2 [\pi_1(1-\pi_1) + \pi_2(1-\pi_2)]}{(\pi_1 - \pi_2 - \delta)^2})$$

adopted and the formula is applied:

六. Data management and confidentiality

Data entry and management were designed in the form of a case report. A case report is a document designed according to the protocol for recording the data of each subject during the

trial.

All records relating to the subject's identity shall be kept confidential and shall not be made public to the extent permitted by applicable laws and/or regulations.

七. Informed consent

The subject of this study is critically illnesses. Before entering the research group, the researchers must obtain the informed consent by the patient or the agent authorizer about the specific content of the study. For details, please refer to the informed consent. The specific procedures for obtaining informed consent include oral and written informed consent from the physician to the patient, patient's family or authorized agent for the above study. The patient volunteered to participate in the study. Patients understand that they can withdraw from the study at any time for no reason, without affecting their future treatment. At the same time, the patient or the agent authorizer will obtain a copy of this informed consent. At the same time, the subjects included in this study were critically illnesses, and the subjects, told and signed, were mainly immediate family members.

八. Report of adverse events

After entering this study, there were some possible adverse reactions:

- (1) Diarrhea, which is most popular, may cause water and electrolyte disturbance in severe cases;
- (2) Nausea and vomiting, and stomach retention;
- (3) High and low blood sugar;
- (4) Aspiration is one of the more serious complications. Patients with weakness, old age or coma are more likely to have liquid diet reflux, especially those with esophageal reflux.
- (5) Take off and plug the pipe.

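### The SAP gives the C-peptide release test no defined response and no pre-feed adjustment, which costs precision or dilutes the effect; the contrast should be reported as a total effect on C-peptide

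*SAP*

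**What the plan says.** The third item under Purpose in the protocol is "Observe the blood sugar and insulin secretion". The Test item under Design and method lists the measurements as "Blood (Microvascular blood sugar+ C-peptide release test), Secretions from the posterior pharynx and trachea". C-peptide is the only named measure that bears on insulin secretion.

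The SAP is one paragraph. For continuous data it says "Student's t test was used for statistical comparison between groups for continuous variables, general linear model for repeated measurement data". It does not mention C-peptide, define an increment or area under the curve, name a covariate, or say which term of the repeated-measures model is tested.

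Three other statements in the protocol bear on how the result can be read:
- The second purpose is "Observe the feeding intolerance and the efficiency of the EN of critically ill patients".
- On the difference between arms: "The treatment of the two groups only depends on whether semi-solid agent was added, while the rest of the treatment measures were consistent".
- On early ending: "If there were serious enteral nutrition complications such as aspiration and abdominal distension within 3 days, the experiment would end".

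**The concern.** A release test is informative through the rise in C-peptide above its pre-stimulus level. The SAP does not derive that rise, and neither of its two methods is given a pre-feed term. No eligibility criterion excludes diabetes, so pre-feed C-peptide is likely to vary widely between patients, and this spread goes into the error term of any comparison that ignores it.

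The SAP also leaves open three analyses of the same samples: a t test at one time point, the group main effect, and the group-by-time term. They estimate different quantities, and the choice could be made after the data are seen.

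The second issue is interpretation. C-peptide responds to the nutrients delivered. Tolerance and efficiency of feeding are themselves study outcomes, and a patient's participation can end early for complications, so delivered feed could diverge after randomisation. An unadjusted contrast would then contain any intake difference, and the SAP does not say how the result is to be described.

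**Working it through.** **Inputs.** The documents give no SD, effect size, correlation or number of samples for C-peptide, so there is no figure of the plan's own to reproduce. Every C-peptide input below is an assumption, shown as a range.

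**1. Post-feed value alone (t test).** The variance of the ANCOVA contrast relative to the post-only contrast is 1 − rho², where rho is the pre/post correlation.
- rho = 0.5: 1 − 0.25 = 0.75, a cut of 25%
- rho = 0.7: 1 − 0.49 = 0.51, a cut of 49%
- rho = 0.8: 1 − 0.64 = 0.36, a cut of 64%

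**2. Change from pre-feed, or group by time (simple pre/post case).** The variance relative to post-only is 2(1 − rho). The ratio of ANCOVA to change is therefore (1 − rho²) / [2(1 − rho)] = (1 + rho)/2.
- rho = 0.5: 0.75, a gain of 25%
- rho = 0.7: 0.85, a gain of 15%
- rho = 0.8: 0.90, a gain of 10%

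**3. Group main effect with the pre-feed sample as a level of the repeated factor.** Suppose there is no effect at the pre-feed sample and a constant effect d at the other k − 1 samples. The main effect then estimates (k − 1)d/k.
- k = 3: 2/3 = 67%
- k = 4: 3/4 = 75%
- k = 5: 4/5 = 80%

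Steps 1 and 3 are alternatives. Step 1 assumes that the pre-feed value is left out, and step 3 that it is in the model, so the two losses cannot be added.

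**4. Intake.** A simulation (3000 runs per setting) took a C-peptide response with no direct treatment effect, a coefficient of 0.6 on the pre-feed value, and a slope b on delivered feed. The expected raw difference is the intake difference times b. The last two columns give how often the t test on the post-feed value rejects at 0.05.

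| Intake difference (SD) | b | Raw difference | 50 per arm | 100 per arm |
|---|---|---|---|---|
| 0 | 0.3 to 0.5 | 0 | 4% to 5% | 5% to 6% |
| 0.5 | 0.3 | 0.15 | 11% | 18% |
| 0.5 | 0.5 | 0.25 | 22% | 42% |
| 1 | 0.3 | 0.30 | 33% | 55% |
| 1 | 0.5 | 0.50 | 69% | 94% |

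ANCOVA on the pre-feed value leaves these differences where they are and only adds precision. Adding delivered feed as a covariate brings the estimate to about 0 with about 5% rejection. If an unmeasured factor drives both intake and C-peptide (loading 0.4, b = 0.3, 100 per arm), that adjustment is itself biased: −0.08 with 13% rejection for an intake difference of 0.5 SD, and −0.16 with 29% for 1 SD.

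**The case against.** The strongest reply is that much of this depends on choices the documents do not state. The SAP does not say that raw concentrations are compared. Its repeated-measures model could include a pre-feed sample and test group by time, which compares change between arms and is not diluted. That stands: the dilution in step 3 applies only if the main effect is read, and against a group-by-time test the gain from ANCOVA is 10% to 25%.

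Randomisation balances pre-treatment C-peptide and diabetes in expectation. That also stands. Ignoring the pre-feed level costs precision and does not bias the comparison.

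A reader might go further and infer that the trial will mistake an intake effect for an effect on insulin secretion. The documents do not support this. It needs a difference in delivered feed at the time of the test, which they neither show nor exclude. Feeding efficiency is undefined, and apart from the agent the arms are meant to be treated alike. With equal intake the simulation shows no bias. If treatment does change intake, the unadjusted contrast is still a valid total effect on C-peptide; only calling it a direct effect on secretion would be wrong, and the documents make no such claim.

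Two further limits stand. The protocol's Study process section has no text in the copy reviewed and a figure under Groups is not shown, so missing sampling times or test-feed details are not held against the plan. And a pre-feed value drawn after study feeding has begun is post-randomisation, so adjusting for it could remove part of a treatment effect.

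What the reply does not answer is that the SAP defines no response, names no baseline term and does not say which term is tested.

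**Conclusion.** The point holds as a gap in the analysis of a secondary purpose. As written, the SAP offers an unadjusted t test or a repeated-measures model with no baseline covariate. Depending on which is used, the cost is one of the following:
- a variance that baseline adjustment would cut by 25% to 64% (post-only t test, assumed rho 0.5 to 0.8);
- a variance that it would cut by about 10% to 25% (change or group-by-time contrast, same rho);
- an estimate diluted to 67% to 80% of a constant effect (group main effect including the pre-feed sample, assumed 3 to 5 samples).

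The precision figures take the test's own pre-feed sample as the covariate. The dilution figures also need that sample to be free of treatment effect, which is assured only if it precedes the first study feed.

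On intake, the conclusion is confined to labelling: the contrast is a total effect that may include any difference in feed delivered. The documents do not establish that such a difference will arise. The sample size calculation concerns feeding intolerance and is not affected.

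**What to change.** In the SAP:
- Define the C-peptide response as the increment, or the incremental AUC, over the test's pre-feed sample.
- Compare arms by ANCOVA with the pre-feed value as a covariate and not as a level of the repeated factor. Use the value drawn before the first study feed where there is one. If only a later value exists, say that it is post-randomisation.
- Report the feed delivered by arm beside the C-peptide result.
- Describe the contrast as a total effect on C-peptide that may include any difference in intake, not as a direct effect on secretion. Do not rely on covariate adjustment for intake to isolate a direct effect, given the bias in step 4.

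The cost is SAP wording, one derived variable, a slightly longer analysis and a table of delivered feed, assuming that the release test includes a pre-feed sample.

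Two additions are optional and left to the sponsor. An index relating C-peptide to glucose would need a rule for incremental glucose near zero or negative, where a ratio is unstable. Standardising the feed used for the test would address intake by design, but it changes the feeding procedure and is not a matter of SAP wording alone.

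### Minor safeguard: analyse repeated outcomes with a mixed model that keeps early stoppers' recorded values, since a general linear model in SPSS by default keeps complete cases only

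*SAP*

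**What the plan says.** The SAP is a single paragraph. For repeated data it specifies a "general linear model for repeated measurement data", and it adds that "All analyses were performed using SPSS 17.0". It does not name the repeated outcomes, define an analysis set or give a rule for missing values.

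The protocol makes incomplete records foreseeable:

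- Section 二(5), Groups: "the treatment time for both groups is 3 days", and "If there were serious enteral nutrition complications such as aspiration and abdominal distension within 3 days, the experiment would end".
- Section 二(4), Abort criteria: these include "Abandoning treatment and discharge, resulting in incomplete data" and "Other condition of researchers think that patients are not fit to continue with the study".
- Section 二(3), exclusion criteria: these include "Stay in ICU less than 3 days" and "No enteral nutrition received for less than 3 days". The second is garbled but seems to concern enteral nutrition lasting under 3 days.

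The likely repeated outcomes are capillary blood glucose and the C-peptide test (section 二(6), Test). They serve the third aim in section 一, Purpose.

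**The concern.** GLM Repeated Measures in SPSS takes one row per patient and by default deletes the whole row if any time point is missing. A patient with a day-1 value who stops before day 3 would contribute nothing.

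This matters if two things hold: the repeated outcome is sampled across the 3 days, and sampling stops with participation. The loss biases the arm comparison if, in addition, stopping depends on the recorded values and its rate or its dependence differs by arm. Unequal rates are conceivable, because the stopping rule names aspiration and the trial asks whether semi-solid feeding reduces aspiration.

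The analysis set matters as much as the model. The SAP does not say whether patients who meet an abort criterion, or who turn out to fall under a 3-day exclusion, stay in the analysis. If they are removed, no choice of model brings their values back.

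**Working it through.** The plan gives no dropout rate, correlation or effect for the repeated outcomes, so it has no figure of its own to reproduce. Only the method, the software, the 3-day period and the stopping provisions come from the documents. Every number below is an assumption or follows from one.

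**1. Values discarded.** Assume 3 daily values and a constant chance h of stopping after day 1 and again after day 2. If a share q stops early, h = 1 − √(1 − q). Per 100 patients:

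- values discarded = 100 × [h + 2h(1 − h)]
- values recorded = 300 × (1 − q) + values discarded

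| q | Discarded / recorded | Share |
|---|---|---|
| 5% | 7 / 292 | 2.6% |
| 10% | 15 / 285 | 5.2% |
| 20% | 29 / 269 | 10.9% |
| 30% | 44 / 254 | 17.2% |

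For example, q = 10% gives h = 0.0513. Discarded values are 5.13 + 2 × 5.13 × 0.9487 = 14.9, and recorded values are 270 + 14.9 = 284.9.

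**2. Bias.** Simulation with 2,000,000 patients per arm, 3 on-treatment times, SD 1, equal correlation between times and no true effect. Here all stopping occurs after the first value, with logit(probability of stopping) = a + slope × first value, and a set to give the required rate. Entries are the size of the complete-case bias in the arm difference, in SD, at times 1 / 2 / 3.

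| Stopping by arm | Slope | Correlation 0.3 | Correlation 0.64 |
|---|---|---|---|
| 16% and 16% | 1 | 0.000 / 0.000 / 0.000 | 0.000 / 0.001 / 0.000 |
| 8% and 16% | 1 | 0.069 / 0.020 / 0.021 | 0.067 / 0.042 / 0.042 |
| 8% and 16% | 0.5 | 0.039 / 0.011 / 0.012 | 0.038 / 0.023 / 0.024 |
| 10% and 20% | 1 | 0.082 / 0.025 / 0.025 | 0.085 / 0.055 / 0.055 |

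Maximum likelihood on all recorded values gives zero bias to within simulation error (about 0.003) in each scenario.

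**3. False-positive rate at nominal 5%, for 8% and 16% stopping.** The test compares the arms on the mean of the 3 times.

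- Mean bias at slope 1: (0.069 + 0.020 + 0.021)/3 = 0.037 for correlation 0.3, and (0.067 + 0.042 + 0.042)/3 = 0.050 for correlation 0.64.
- SD of a patient's mean: √[(1 + 2ρ)/3] = 0.730 and 0.872.
- SE = SD × √[1/(0.84n) + 1/(0.92n)], with n randomised per arm.
- Rate = Φ(−1.96 − k) + Φ(−1.96 + k), where k = bias/SE.

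At n = 50 the SEs are 0.156 and 0.186, k is 0.24 and 0.27, and the rate is 5.6% to 5.8%. At n = 100 it is 6.3% to 6.7%. At n = 200 the SEs are 0.078 and 0.093, k is 0.47 and 0.54, and the rate is 7.6% to 8.4%. At slope 0.5 the mean biases are 0.021 and 0.028. The rate then runs from 5.2% (n = 50, k = 0.021/0.156 = 0.13) to 6.1% (n = 200, k = 0.028/0.093 = 0.30).

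**4. Precision.** The complete-case SE is 2% to 4% larger than the likelihood SE at the first time and 0 to 2% larger later, so precision is a side issue.

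**5. Would a smaller change do?** Adding a pre-treatment covariate to the complete-case model leaves 0.04 to 0.06 SD at the first on-treatment time and about 0.02 SD later (8% and 16%, slope 1).

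**6. Where the mixed model falls short.** If stopping depends on an unrecorded second value (8% and 16%), the bias at that time is 0.066 SD complete-case and 0.061 SD by likelihood at correlation 0.3, and 0.068 and 0.043 SD at correlation 0.64.

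**The case against.** The strongest reply is that the premise is not in the readable text. The section headed Study process (三) is empty there and a figure under Groups is not shown, so a sampling schedule may exist where it cannot be read. The SAP does not say which variable goes to the general linear model. If it is the C-peptide test and all samples come from one session, early stopping costs almost nothing and both models use the same patients. Ending the experiment may also end treatment but not sampling. All of this stands, and it is why the point is conditional. The absence of a readable schedule should not be reported as a defect of the plan.

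Second, no document ties stopping to glucose or C-peptide. A reader might infer that the planned analysis is biased, but the documents do not support that: the unequal rates and the dependence in the working are assumed.

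Third, a reader might put the 30.8% intolerance rate into the sample-size formula for both arms, obtain more than a thousand patients per arm, and infer a far larger false-positive rate. The readable text states no such sample size. The result depends on assuming equal rates and on how the Z term is read (1,621 per arm literally, 1,339 with z = 1.96), and the formula was written for feeding intolerance. Such rates should not be used.

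Fourth, one might say that the two 3-day exclusions can only be known after entry. That is too strong. The ICU criterion could refer to expected or prior stay, and the nutrition criterion is too garbled to date. It is enough that the text leaves room for either to be applied after randomisation.

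Finally, the mixed model leaves about 63% to 92% of the bias when stopping follows an unrecorded value (0.043/0.068 and 0.061/0.066). This limits the fix, but the complete-case model does no better there.

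**Conclusion.** The point holds as a low-priority, conditional safeguard, with medium confidence. It most likely concerns the third-listed aim on blood sugar and insulin secretion, not the complication outcomes.

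If sampling spans the 3 days and stops with participation, the natural reading of the SAP discards recorded values. For that to bias the comparison, stopping must depend on those values and must differ by arm in rate or dependence. Under assumed 8% and 16% stopping, the bias is about 0.04 to 0.07 SD at the first time and 0.01 to 0.04 SD later. The false-positive rate is about 6% to 8% at an assumed 50 to 200 patients per arm under the stronger dependence, and 5% to 6% under half of it. With equal rates and dependence the bias is zero. It would be wrong to read this as a shown error, or to expect a change of model alone to cure informative stopping.

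**What to change.** In the SAP:

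1. Analyse repeated outcomes with a likelihood-based linear mixed model (SPSS MIXED, REML) with arm, time, arm-by-time and the pre-treatment value where measured. Use all recorded values from all randomised patients.
2. State that patients who meet an abort criterion, or who are found after randomisation to meet the under-3-days ICU-stay or enteral-nutrition criterion, keep their recorded values in this analysis unless consent to use the data is withdrawn. Without this sentence the model change restores nothing.
3. Report missing values by arm and time.
4. Add one sensitivity analysis for missingness that depends on unrecorded values.

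Cost: three or four sentences, slightly more analysis work and no new software. The model relies on missing-at-random, which may not hold. It gains nothing if all samples come from one session, so check the sampling schedule in the full protocol first. No clinical rule is affected.

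### The sample size is set for non-inferiority on feeding intolerance, but the SAP contains only tests of no difference, with no margin, confidence interval or decision rule

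*SAP*

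**What the plan says.** Protocol section 五 (Sample Size Calculating) takes its rate from the literature: "the incidence of gastrointestinal intolerance (FI) is about 30.8" per cent. It then sets δ = -0.05, α = 0.025 and β = 0.20, and says that "the non-inferior efficiency test design is" adopted. The formula has π₁ − π₂ − δ in its denominator and Z at 1 − α/2 in its numerator. The readable text shows no rate for the second arm and no resulting N, and does not say which group is group 1.

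The SAP is one paragraph. It assigns the t test to continuous variables, a general linear model to repeated measurements, and "Fisher exact tests for categorical variables, and Mann-Whitney U test for ordinal variables". One alpha of 0.05 covers every test. Non-inferiority, a margin, a confidence interval and the sidedness of the tests are not mentioned.

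The objectives in Protocol section 一 point in two directions. Purpose 1 is worded as superiority: "To investigate whether intermittent feeding with semi-solid nutrients improves the enteral nutrition complications of diarrhea, reflux and aspiration". FI, the outcome used for sizing, appears only in Purpose 2: "Observe the feeding intolerance and the efficiency of the EN of critically ill patients".

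**The concern.** A non-inferiority sample size is built to reject the hypothesis that IS is worse than ordinary intermittent feeding (IF) by at least the margin. Fisher's exact test has a different null hypothesis, that the two rates are equal. If IS and IF perform alike, which is where non-inferiority matters most, Fisher will nearly always be non-significant. That result cannot be read as non-inferiority, because it says nothing about whether a 5-point harm has been excluded.

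As the documents stand, a reader cannot tell which result would make the trial positive. An interval could be calculated afterwards from the reported proportions, but its level and the margin applied to it would not have been pre-specified in the analysis plan.

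**Working it through.** **Inputs from Protocol section 五.** Reference FI rate 0.308; δ = -0.05; α = 0.025; β = 0.20, so power 0.80 and z = 0.842; equal arms.

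**Assumptions.** The IS rate is not given, so a range is used. π is taken as the FI-free proportion with IS as group 1, which makes δ = -0.05 a margin against harm. The sidedness of α is not stated, so two readings of Z are carried: 1.960 (α = 0.025 one-sided) and 2.241 (the printed 1 − α/2 taken literally). There is no published N to reproduce.

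**Step 1: size at equal rates.** The printed formula is n = (Z + 0.842)² × [π₁(1 − π₁) + π₂(1 − π₂)] / (π₁ − π₂ − δ)².

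- Variance term: 2 × 0.308 × 0.692 = 0.4263. Denominator: 0.05² = 0.0025.
- Z = 1.960: 1,338.3, so 1,339 per arm.
- Z = 2.241: 1,620.7, so 1,621 per arm.

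**Step 2: what each analysis delivers at those sizes.** Exact enumeration of the binomial tables with both true rates at 30.8% gives:

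- Upper limit of a Newcombe interval for IS minus IF below +5 points, at the matching level (95% or 97.5%): about 80% in both cases.
- Two-sided Fisher at 0.05 significantly favouring IS: about 2% in both cases. This is the only Fisher outcome that supports non-inferiority.

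**Step 3: the same N, with IS truly better.** Probability that Fisher significantly favours IS:

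| True IS rate | 1,339 per arm | 1,621 per arm |
|---|---|---|
| 28.8% | 19% | not enumerated |
| 26.8% | 61% | 70% |
| 25.8% | 81% | 88% |
| 20.8% | about 100% | not enumerated |

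At 1,339 per arm, 80% is reached only at a true benefit of about 5 points.

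**Step 4: N set from the formula at a lower assumed IS rate.** The denominator grows with the assumed benefit, so N falls. At IS 25.8%, for example, it is (0.05 + 0.05)² = 0.01.

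| Assumed and true IS rate | n per arm, z = 1.960 | Fisher favours IS | n per arm, z = 2.241 | Fisher favours IS |
|---|---|---|---|---|
| 28.8% | 670 | 11% | 812 | 13% |
| 25.8% | 318 | 26% | 385 | 31% |
| 20.8% | 132 | 41% | 160 | 49% |
| 15.8% | 68 | 48% | 83 | 57% |

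The matching Newcombe interval succeeds in about 80% of trials in every row.

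**Step 5: if superiority on FI is what is meant.** A continuity-corrected two-proportion formula (two-sided 0.05, 80% power), with the exact Fisher power in brackets, gives 1,313 per arm at IS 25.8% (0.800), 320 at 20.8% (0.803) and 137 at 15.8% (0.807).

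- Against the equal-rates size: 1,313 / 1,339 = 0.98, and less for larger benefits.
- Against the Step 4 sizes at z = 1.960: 1,313 / 318 = 4.1; 320 / 132 = 2.4; 137 / 68 = 2.0.

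**Direction of δ.** If π were FI incidence with IS as group 1, the denominator at IS 25.8% would be (-0.05 + 0.05)² = 0 and no sample size would exist. The definition of π therefore has to be stated.

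**The case against.** The best counter-argument is that the numerical consequences depend on an N and an IS rate that nobody can see. That limits four stronger readings that a reader might infer.

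- **That Fisher would usually miss a moderate benefit.** This holds only if N was reduced in line with the assumed benefit (Step 4). If N was set at equal rates, a true 5-point benefit would be detected in 81% to 88% of trials (Step 3). The documents do not say which applies.
- **That a superiority trial would need 2 to 4 times as many patients.** This rests on the same pairing. Against the equal-rates size, no more patients would be needed for a benefit of 5 points or more.
- **That the protocol never defines FI or names a primary endpoint.** Neither is found in the readable text, but a figure under Groups is not shown and the Study process heading has no readable content. Absence from the full document cannot be asserted.
- **That the alphas of 0.025 and 0.05 conflict.** They agree if the first is one-sided and the second two-sided. The Z subscript points the other way but may be a slip. This is secondary.

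It is also fair to say that the protocol prints β and never states a power, and that the choice among standard interval methods is a preference. None of this removes the mismatch: the sizing tests against a margin and the SAP does not, whatever N turns out to be.

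**Conclusion.** The plan is wrong as written. Sizing and analysis address different hypotheses, and the planned analysis cannot draw the conclusion for which the trial is sized. The documents do not settle whether the fault lies in the sizing section or in the SAP.

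The mismatch itself needs no assumed rates; its size does. At equal rates of 30.8%, the contrast is about 80% for the matching interval against about 2% for Fisher, under either reading of Z. Away from equal rates, Fisher's power ranges from low to adequate according to how N was fixed. No general statement about its power, or about the patients that superiority would need, is supported. This must be resolved before analysis, because otherwise the main conclusion has no pre-specified basis.

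**What to change.** First state whether the hypothesis is non-inferiority or superiority and on which endpoint. If that endpoint is FI, define it. Then take one of two routes.

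**If non-inferiority on FI is kept:**

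- Add to the SAP a two-sided confidence interval for the risk difference IS minus IF (for example Newcombe or Miettinen-Nurminen). Match its level to the sizing alpha: 95% if 0.025 is one-sided, 97.5% if the printed Z is meant.
- Conclude non-inferiority only if the upper limit is below +5 points, and superiority if it is also below 0.
- Define π, the group order and the direction of δ in Protocol section 五.
- State that a non-significant Fisher test is not evidence of non-inferiority, and keep Fisher for superiority comparisons.

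The cost is SAP wording and one interval, with no new data.

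**If superiority is intended:** remove the non-inferiority wording and restate the sizing basis and power for the chosen endpoint. Whether this raises the number of patients cannot be told until N and the assumed IS rate are stated.

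### Reflux and aspiration get only unadjusted Fisher tests although the protocol names risk factors for reflux; the loss is modest precision, not bias

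*SAP*

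**What the plan says.** The SAP is one paragraph. For binary outcomes it lists "Fisher exact tests for categorical variables". Its only model is a "general linear model for repeated measurement data", with no covariates named, and it adds that "All tests for statistical significance were determined using an alpha level of 0.05". It does not name reflux or aspiration. That they fall under the Fisher test is inferred from their being yes/no events.

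The protocol's section 一 (Purpose), item 1, asks whether semi-solid feeding "improves the enteral nutrition complications of diarrhea, reflux and aspiration". Section 八 (Report of adverse events), item (4), opens with "Aspiration is one of the more serious complications" and continues: "Patients with weakness, old age or coma are more likely to have liquid diet reflux, especially those with esophageal reflux". The inclusion criterion "not less than 14 years old of critical illnesses" means that age is known at enrolment.

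Section 五 (Sample Size Calculating) plans a non-inferiority comparison on feeding intolerance (FI): rate 30.8%, δ = -0.05, α = 0.025, β = 0.20. No resulting n appears.

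**The concern.** The sponsor itself names patient characteristics that make reflux more likely. They can be recorded before feeding starts, and two of them, age and coma, should be known at enrolment in any case. Adjusting for pre-treatment factors that predict the outcome narrows the confidence interval without adding patients, and corrects the estimate when one arm has, by chance, more patients at high risk. An unadjusted Fisher test does neither. If adjustment is not pre-specified, any made after an imbalance is seen will be post hoc and hard to defend.

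A second, separate point concerns FI. The sample size rests on a 5-point margin, but a Fisher p-value tests equality and gives no interval to set against that margin. An unadjusted interval would cure this, so it is not an argument for covariate adjustment.

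**Working it through.** The documents state no n, event count or achieved power, so there is no figure of the plan's to reproduce. The steps below show scale only.

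**1. The n implied by the protocol's inputs.** With π₁ = π₂ = 0.308 (equal rates are an assumption) and one-sided α = 0.025:

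n = (1.960 + 0.842)² × 2 × 0.308 × 0.692 / 0.05² ≈ 1,339 per arm.

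The printed formula uses α/2, which gives 1,621 per arm.

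**2. Precision gain.** If covariates explain a share R² of outcome variance, the variance of the adjusted difference is roughly multiplied by (1 − R²). Assumed values, none from the documents: coma in 40% with odds ratio (OR) 2 to 4; age OR 1.25 to 2 per SD; esophageal reflux in 15% with OR 2 to 3; event rate 30.8%. The rate is the FI figure, borrowed because none is given for reflux or aspiration. A simulated population of 1,000,000 gives R² = 0.048 for the weak set and 0.18 for the strong set. Then

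power = Φ(2.802/√(1 − R²) − 1.960)

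- R² = 0.048: 81.9%
- R² = 0.18: 87.2%

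**3. The same gain in small arms, against the 5-point margin.** SE = √(2 × 0.308 × 0.692/n); power = Φ(0.05/(SE√(1 − R²)) − 1.960).

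| n per arm | SE (points) | Unadjusted | R² = 0.048 | R² = 0.18 | Gain (points) |
|---|---|---|---|---|---|
| 50 | 9.2 | 7.8% | 8.0% | 8.7% | 0.2 to 0.9 |
| 100 | 6.5 | 11.6% | 12.0% | 13.3% | 0.4 to 1.7 |

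**4. Chance imbalance in coma.** With 40% prevalence, the SD of the between-arm difference is √(2 × 0.4 × 0.6/n): 9.8 points at n = 50 and 6.9 at n = 100. A difference of 10 points or more, in either direction, occurs in 31% and 15% of trials, and practically never at 1,339. Under the assumed ORs, risk differs between comatose and other patients by about 15 to 26 points. A 10-point imbalance therefore moves the raw risk difference by 1.5 to 2.6 points. That is 0.16 to 0.28 SE at 50 per arm and 0.23 to 0.40 SE at 100.

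**5. Simulated superiority test.** 4,000 runs per scenario, one binary factor, conditional OR for treatment 0.45 (assumed), two-sided 0.05. R² = q(1 − q)(p₁ − p₀)²/[m(1 − m)], where q is the factor's prevalence, p₀ and p₁ the control-arm risks without and with it, and m the mean risk.

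- Moderate: p₀ = 25%, p₁ = 45%, q = 30%, m = 31%; R² = 0.21 × 0.04/0.2139 = 0.04
- Strong: p₀ = 15%, p₁ = 55%, q = 40%, m = 31%; R² = 0.24 × 0.16/0.2139 = 0.18

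| Factor | n per arm | Fisher | Unadjusted chi-square | Stratified Mantel-Haenszel |
|---|---|---|---|---|
| Moderate | 50 | 29% | 37% | 37% |
| Moderate | 100 | 57% | 63% | 65% |
| Moderate | 200 | 88% | 90% | 91% |
| Strong | 50 | 23% | 30% | 33% |
| Strong | 100 | 47% | 53% | 60% |
| Strong | 200 | 79% | 82% | 88% |

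With no treatment effect, Fisher rejected in 3.2% to 4.4% of runs and the stratified test in 4.6% to 5.4%. Stratifying adds 0 to 2 power points over chi-square for the moderate factor and 3 to 7 for the strong one. The larger gap to Fisher, 3 to 13 points, is partly Fisher's own conservatism.

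**The case against.** The strongest reply is that the plan is valid as it stands. The trial is described as a "Single center, randomized, single blind, controlled prospective study". Under randomisation, chance imbalance is already allowed for in the Fisher test's type I error, and the simulation bears this out. A reader might infer that an unadjusted comparison would be biased, or that an excess of comatose patients would invalidate it. The documents do not support that, and this reply stands.

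Three further limits also stand:

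- **Scope.** The protocol ties the factors to reflux, within the item on aspiration. A reader might extend them to diarrhea or FI, but nothing in the documents makes that link. The illustration also has to borrow the FI rate.
- **The two harms do not peak together.** The rise from 80% to 82–87% belongs to about 1,339 per arm, where imbalance is negligible. Sizeable imbalance belongs to 50 to 100 per arm, where power against the margin is about 8% to 12% before adjustment and scarcely moves.
- **Stratification.** It is tempting to say that randomisation ignored these factors. The text read describes no stratification, but a figure under Groups is not shown and the Study process section carries no text here. The point therefore rests on the SAP's silence alone.

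What the reply does not remove is that the sponsor has named predictors of reflux, the SAP makes no use of them, and pre-specifying their use costs little.

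**Conclusion.** The point holds as a recommendation about efficiency and robustness for reflux and aspiration. It is not a finding of bias or invalidity. Its size is uncertain because prevalence, prognostic strength, outcome rates and n are all assumed. Under those assumptions, 5% to 18% of variance explained lifts a nominal 80% power to about 82% to 87%. The gain is near zero if the factors are weak, and under 2 points against the 5-point margin at 50 to 100 per arm.

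The FI point depends on none of these assumptions. The protocol sets a margin, and the planned test cannot address it.

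**What to change.** In the SAP:

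- **Reflux and aspiration.** Make the main comparison a logistic model with arm, age (continuous), coma at enrolment (yes/no) and history of esophageal reflux (yes/no). Report the standardised IS minus IF risk difference with 95% CI.
- **Few events.** Pre-specify a fallback, a Mantel-Haenszel risk difference stratified by coma, and the event count that triggers it.
- **Fisher test.** Keep it as an unadjusted check.
- **Weakness.** The protocol names it too. Either define a baseline measure and include it, or say why it is left out.
- **Feeding intolerance.** Report the IS minus IF risk difference with 95% CI and compare it with the 5-point margin. State the direction: FI is an unwanted event, so on this coding the limit to check is the upper one. A 95% CI matches α = 0.025 read as one-sided; the α/2 in the printed formula should be reconciled with it.

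The cost is two yes/no baseline items on the case report form, a few SAP lines, a model to fix in advance and a rule for rare events. No extra patients are needed.
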